8.2.1. Assessing Objective Tumor Response (RECIST v1.1)

- A comprehensive workup will be performed at baseline, and every 12 weeks.
- Whenever response criteria are met, the appropriate imaging tests will be repeated at least four weeks later in order to confirm the response.
- The same method will be used to evaluate each identified lesion both at baseline and throughout the study.
- Treatment will be administered as long as no disease progression or unacceptable toxicity is found, or as long as no other reasons for treatment discontinuation are met.
- Assessment of efficacy will be essentially based on a set of measurable lesions identified at baseline as target lesions and followed until disease progression and following the RECIST v1.1 criteria (Eisenhauer, 2009).

8.2.2. Centralized Radiological Review (Institut Bergonié)

8.2.2.1. GENERAL PROCEDURE

Centralized radiological review will be performed to confirm disease status at 6 months in comparison with baseline, Week#12 and Week#24 and every 8 weeks for patients with metastatic disease at inclusion. For patients included in the reference center, MRI and CT scan (for patients with metastatic disease) will be initially read by a radiologist who differs from the expert.

Review process will be centralized at Institut Bergonié and will be performed by a radiologist expert in

soft tissue sarcomas.

In case of discordance between the local radiologist and the expert reviewer, the judgment provided by the expert reviewer will be retained and used in statistical analyses.

8.2.2.2. REVIEW PROCESS SCHEDULE

All tumor evaluations will be sent as soon as there were available.

Patient's information must be recorded on a provided imaging CD.

8.2.2.3. PRACTICAL IMPLEMENTATION

For each shipment, each media should be accompanied by the Radiological Forms provided by the sponsor.

All CDs must be sent as described in a specific SOP provided by the Sponsor.

8.3.SAFETY

Patients will be evaluable for safety if they have received at least one treatment administration. Safety will be evaluated using clinical examinations, which will comprise vital signs analysis, clinical assessment of AEs, changes in laboratory parameters (hematological and biochemical, including liver function tests) and any other analyses that may be considered necessary. Safety profile will be continuously followed during treatment up to 30 days after the last treatment administration or until the start of a new antitumor therapy, whichever occurs first, and/or 6 weeks after the last dose of radiotherapy. All AEs will be classified according to the NCI-CTCAE, version 4.0.

Note: if surgery performed, patient will be followed up at D30, D60 and D90 post surgery.

9. STUDY ENDPOINTS

9.1.DOSE ESCALATION

Primary endpoint

- Toxicity graded using the common toxicity criteria from the NCI v4.03.
- Incidence rate of DLT at each dose level during treatment period up to six weeks after end of radiotherapy.

Secondary endpoints

Antitumor activity observed with Olaparib given in association with radiotherapy in terms of

- 6-month non progression, defined as complete (CR) or partial response (PR) at 6 months confirmed ≥ 4 weeks after initial documentation, or stable disease more than 24 weeks (RECIST v1.1, as determined by investigator review of tumor assessments)
- 6-month objective response, defined as CR or PR at 6 months confirmed ≥ 4 weeks after initial documentation, as determined by investigator review of tumor assessments using RECIST v1.1
- Best objective response under treatment is defined as complete (CR) and partial response (PR) recorded from the start of study treatment until the treatment with confirmation ≥ 4 weeks after initial documentation, as per RECIST 1.1. Objective response under treatment is determined once all the data for the patient is known.
- Best response under treatment is defined as the best response (CR, PR, SD) as per RECIST 1.1 recorded from the start of the study treatment until the end of treatment taking into account any requirement for confirmation as per RECIST v1.1 criteria. It is determined once all the data for the patient is known.
- 1-year Progression-free survival (PFS): PFS is defined as the time from study treatment initiation to the first occurrence of disease progression or death (of any cause), whichever occurs first.
- 1-year Overall Survival (OS): OS is defined as the time from study treatment initiation to death (of any cause).
- Functional assessment
 - Graded using the Musculoskeletal Tumour Society Rating Scale (Enneking, Modification of the system for functional evaluation in the surgical management of musculoskeletal

turnours. In: Enneking WF, ed. Limb Salvage in Musculoskeletal Oncology. New York, NY: Churchill Livingstone, 1987:626A39.

- MSTS will be completed by the radiotherapist at baseline and at the end of radiotherapy treatment.
- The MSTS score is calculated from 6 functional criteria.
 - Three subjective criteria are common to the upper and lower limbs: pain, function, emotional acceptance of the surgical procedure (psychological acceptance).
 - The other three are objective criteria:
 - For the lower limb: support, walking and gait.
 - For the upper limb: the position relative to shoulder, dexterity, muscle strength
 - Each criterion is evaluated with a question (eg, pain is assessed by the consumption of analgesic drugs). The evaluation of each test contains six levels of achievement or scores, four defined scores (0, 1, 3, 5) and two intermediate (2, 4). The four scores are defined the score 5: absence of impact; the score 3: minor impact; the score 1: major repercussions; the score 0: disability.
- Concerning the analysis of MSTS,
 - The total score will be described at each measurement time
 - A difference of 10 points or more will be used to define a clinically significant difference. There is particular focus on the difference between the observed scores before surgery and 1 year post surgery.
- PK measurements expressed as AUC, half-life and concentration peak for Olaparib.

9.2.EXPANSION COHORT

Primary endpoint

6-month non progression as defined for the dose escalation part. For the expansion cohort, radiological data will be centrally reviewed. The primary analysis will be based on reviewed data.

Secondary endpoints

- Antitumor activity observed with Olaparib given in association with radiotherapy in terms of 6-month objective response, best response under treatment, best objective response under treatment, 1-year PFS and 1-year OS, as defined for the dose escalation part.
- Toxicity graded using the common toxicity criteria from the NCI v4.03.
- PK measurements expressed as AUC, half-life and concentration peak for Olaparib.
- Pharmacodynamics (translational research): Prognostic markers of anti-tumor activity of Olaparib given with concomitant radiotherapy will be investigated.

10.STATISTICAL CONSIDERATIONS

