4. SELECTION OF PATIENTS

4.1. INCLUSION CRITERIA

1. Histology: patients with soft-tissue sarcoma histologically confirmed by central review (Pr [name] team), except if the diagnosis was already confirmed by the RRePS Network,
2. Upper/Lower limb or trunk wall soft-tissue sarcoma,
3. Age ≥ 18 years,
4. Locally advanced or locally recurrent primitive tumor, outside any previously irradiated field. Patients presenting operable locally advanced or locally recurrent tumor can be included. Patients with metastases can be included in the protocol,
5. Eastern Cooperative Oncology Group (ECOG), performance status ≤ 2 ,
6. Life expectancy ≥ 6 months,
7. At least one lesion, not previously irradiated, that can be accurately measured at baseline as ≥ 10 mm in the longest diameter (except lymph nodes which must have short axis ≥ 15 mm) with magnetic resonance imaging (MRI) and which is suitable for accurate repeated measurements,
8. Adequate hematological, renal, metabolic and hepatic function:
 - Haemoglobin ≥ 9 g/dL and no blood transfusions in the 14 days prior to study entry
 - Absolute neutrophil count (ANC) $\geq 1.5 \times 10^9/L$
 - Platelets $\geq 100 \times 10^9/L$
 - Total bilirubin $\leq 1.5 \times$ upper limit of normality (ULN),
 - Alanine aminotransferase (ALAT) or aspartate aminotransferase (ASAT) $\leq 2.5 \times$ ULN,
 - Serum creatinine $\leq 150 \mu\text{mol/L}$ or creatinine clearance $\geq 50 \text{ mL/min}$ (according to local institution) in case of serum creatinine $> 150 \mu\text{mol/L}$,
 - TP, INR $\leq 1.5 \times$ ULN
9. Women of childbearing potential must have a negative serum pregnancy test within 28 days of study treatment, confirmed prior to treatment on day 1. Female patients of child bearing potential and their partners, who are sexually active, must agree to the use of two highly effective forms of contraception in combination throughout the period of taking study treatment and for at least 1 month after last dose of study drug. Males patients, who are sexually active, and their partners of child bearing potential must agree to the use of two highly effective forms of contraception in combination throughout the period of taking study treatment and for at least 3 month after last dose of study drug. Acceptable birth control methods are described in appendix 6. Subjects of non-childbearing potential are those who have:
 - Amenorrheic for 1 year or more following cessation of exogenous hormonal treatments,

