APPENDIX 7: MUSKULOSKELETAL TUMOR SOCIETY FUNCTIONAL FORM

SCORE	PAIN	FUNCTION	EMOTIONAL	SUPPORTS	WALKING	GAIT	Final Patient
5	No pain	No restriction	Enthused	None	Unlimited	Normal	Score of FUNCTIONAL EVALUATION
4	Intermediate	Intermediate	Intermediate	Intermediate	Intermediate	Intermediate	
3	Modest/Non-disabling	Recreational restriction	Satisfied	Brace	Limited	Minor cosmetic	
2	Intermediate	Intermediate	Intermediate	Intermediate	Intermediate	Intermediate	
1	Moderate/Disabling	Partial restriction	Accepts	One cane or crutch	Inside only	Major cosmetic	
0	Severe disabling	Total restriction	Dislikes	Two canes or crutches	Not independent	Major handicap	
Patient score

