    - Each criterion is evaluated with a question (eg, pain is assessed by the consumption of analgesic drugs). The evaluation of each test contains six levels of achievement or scores, four defined scores (0, 1, 3, 5) and two intermediate (2, 4). The four scores are defined the score 5: absence of impact; the score 3: minor impact; the score 1: major repercussions; the score 0: disability.
  - Concerning the analysis of MSTS,
    - The total score will be described at each measurement time
    - A difference of 10 points or more will be used to define a clinically significant difference. There is particular focus on the difference between the observed scores before surgery and 1 year post surgery.
- PK measurements expressed as AUC, half-life and concentration peak for Olaparib.

Criteria	eFORM variable	Control
6-month non progression	TUM_CYC (TUMOR ASSESSMENT) DT_MEAC (date of measurement) ME1L_ME5L (measures of lesions) SUM_TL (largest diameters) EVA1LNM_EVA5LNM (non-measurable lesions eval) RES_TL, RES_NTL (target and non-target lesions) OV_RESP (overall response) CR=1, PR=2, SD=3 TRT_OLA DT_S10 (D1 Olaparib)	DT_S10 filled in ME1L_ME5L (filled in if needed) SUM_TL filled in EVA1LNM_EVA5LNM (filled in if needed) RES_TL, RES_NTL (filled in) and check recist1.1 criteria  check for each patient (( DT_MEAC-DT_S10 ≥ 6 ) and OV_RESP =(1 or 2 or 3))  Check confirmation ≥ 4 weeks  Count number of non-progression case

6-month objective response	TUM_CYC (TUMOR ASSESSMENT) DT_MEAC (date of measurement) ME1L_ME5L (measures of lesions) SUM_TL (largest diameters) EVA1LNM_EVA5LNM (non-measurable lesions eval) RES_TL, RES_NTL (target and non-target lesions) OV_RESP (overall response) CR=1, PR=2 TRT_OLA DT_S10 (D1 Olaparib)	DT_S10 filled in ME1L_ME5L (filled in if needed) SUM_TL filled in EVA1LNM_EVA5LNM (filled in if needed) RES_TL, RES_NTL (filled in) and check recist1.1 criteria  check for each patient (( DT_MEAC-DT_S10 ≥6 ) and OV_RESP =(1 or 2))  Check confirmation ≥ 4 weeks  Count number of objective case

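### The supplied MSTS form lacks the upper-limb items that section 9.1 requires, trunk-wall patients have no objective items, and one item presupposes surgery, so totals outside the lower limb are unreliable

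*Protocol*

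**What the plan says.** Eligibility (Protocol 4.1) covers "Upper/Lower limb or trunk wall soft-tissue sarcoma". Function before and after treatment is a secondary objective of both parts (Protocol 2.2.1 and 2.2.2).

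The instrument is described in Protocol 9.1 and repeated in SAP 3.2.2.1: "The MSTS score is calculated from 6 functional criteria". Three items are common to both limbs: pain, function, and "emotional acceptance of the surgical procedure (psychological acceptance". The other three depend on the limb:

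- "For the lower limb: support, walking and gait"
- "For the upper limb: the position relative to shoulder, dexterity, muscle strength"

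Each item runs from 0 to 5. The form in Protocol Appendix 7 has six columns: pain, function, emotional, supports, walking and gait. Its lowest supports grade, for example, is "Two canes or crutches".

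The score is taken at baseline and at the end of radiotherapy (Protocol 5.5 and 9.1, and the schedule footnote). Surgery, where it is done, follows within 12 weeks of completing radiotherapy (Protocol 7.3).

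For the analysis, the total is described at each time point, and "A difference of 10 points or more will be used to define a clinically significant difference". Both documents then single out the comparison of scores before surgery with scores one year after it. The SAP's only check is that a single variable, MSTS_RA, has been completed.

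**The concern.** The definition and the form disagree for the upper limb, and neither covers the trunk wall. An arm scored on supports, walking and gait earns points for the patient's legs, so loss of arm function during treatment may not show in the total. Protocol 7.2.5 expects the acute toxicity of this radiotherapy to be mainly musculoskeletal and cutaneous, so loss of local function is what the score should be able to detect. The likely error runs towards no change.

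The emotional item adds a second problem. As section 9.1 words it, it asks about an operation that the study has not yet performed at either scheduled visit, and that patients with unresectable tumours may never have. Sites could leave it blank, score it for an earlier operation, or score general acceptance. The SAP has no rule for a missing or inapplicable item, and states that missing data are not imputed.

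Totals may therefore mean different things in different patients and at different sites, while one threshold is applied to all of them.

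**Working it through.** The documents give no derivation, standard deviation or sample size for MSTS, so the 10-point threshold cannot be reproduced. What can be checked is whether the scale allows it to be reached.

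**Inputs.** Six items, each scored 0–5, and a threshold of 10 points (Protocol 9.1); the columns of the form (Appendix 7).

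**Assumptions.** (a) The total is the raw sum. (b) An upper-limb or trunk-wall patient with unaffected legs scores 5 on supports, walking and gait at both visits. (c) The emotional item is scored, unless stated otherwise.

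**Range.** The maximum is 6 × 5 = 30. Under (b), 3 × 5 = 15 points are fixed. The total cannot fall below 15, and 30 − 15 = 15 points can move.

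**Size of the threshold.**
- Six site-appropriate items: 10/30 = 33% of the range, an average of 10/6 = 1.67 levels per item.
- Supplied form, legs unaffected: 10/15 = 67% of the movable range, an average of 10/3 = 3.33 levels per item.

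**Baseline profiles from which a 10-point fall is possible.** With k movable items there are 6^k profiles. A fall of 10 is possible only if the movable items sum to at least 10 at baseline.

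| Setting | k | Profiles with sum ≥ 10 | All profiles | Share |
|---|---|---|---|---|
| Six site-appropriate items | 6 | 42,155 | 46,656 | 90% |
| Five site-appropriate items (emotional item not scored) | 5 | 6,054 | 7,776 | 78% |
| Supplied form, legs fixed at 5 | 3 | 56 | 216 | 26% |

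By symmetry of the 0–5 items, the share from which a 10-point rise is possible is the same in each row. The shares describe the scale, with every profile counted equally. They do not predict how many patients would cross the threshold.

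**Effect of the unstated scale.** If the 10 points refer to a 0–100 score, they equal 10 × 30/100 = 3 raw points. That is easy to reach, even with 15 points fixed.

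**Trunk wall.** Section 9.1 gives objective items for the lower limb and for the upper limb only. Three of the six items are therefore undefined for these patients in the text, the form and the SAP.

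**Timing.** The scheduled scores are baseline and end of radiotherapy. The featured comparison needs a score one year after surgery. The three added post-surgery visits (D30, D60 and D90) are described as clinical examinations, and no MSTS is planned at one year. The comparison has no second measurement.

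**The case against.** **The upper-limb page may exist.** The available protocol text also lacks Appendix 5 (cited in section 11.4) and sections 6–8 of the serious adverse event form, so a second MSTS page could have been lost in the same way. This stands as a real possibility, and the first step is to check. It does not affect the trunk-wall gap, the surgery item, the unstated scale or the missing one-year score.

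**Upper-limb totals can be computed.** A reader might infer that the form holds only lower-limb items and that upper-limb totals cannot be formed. The documents do not support that. Three of the six columns are the common items, and section 9.1 names the upper-limb ones. A site that uses those obtains a proper total; it goes wrong only if Appendix 7 is used as supplied.

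**The threshold is not generally out of reach.** A reader might also infer that 10 points can hardly ever be reached. For lower-limb patients, and for correctly scored upper-limb patients, it is reachable from 90% of profiles (78% without the emotional item). It comes close to impossible only if three assumptions are stacked: the wrong form, legs fixed at 5 and the emotional item unscored. Pain and function must then both fall from 5 to 0, which is possible from 1 of 36 profiles. That extreme should not stand for the plan, and a percentage scale would reverse the picture.

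**The emotional item may be answerable.** The Appendix 7 column is headed simply as emotional, and section 9.1 also glosses it as psychological acceptance. No document says that it is left blank before surgery. This stands, so the 26% and 90% figures keep the item in. The section 9.1 definition still refers to surgery and needs a rule.

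**The impact is small.** The endpoint is descriptive and drives no decision. It appears in none of the SAP's listed tables, and the number of upper-limb and trunk-wall patients is not given. This stands and sets the severity.

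**Conclusion.** The point holds, and is minor. As supplied, Appendix 7 does not match section 9.1 for the upper limb, trunk-wall patients have no defined objective items, and one common item is defined by surgery that has not taken place at either scheduled score.

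On a raw 0–30 sum, with the form used as it stands and the legs unaffected, half the points are fixed and the share of profiles from which a 10-point fall is possible drops from 90% to 26%. That figure depends on all three conditions and does not apply to lower-limb patients. The size of any bias in the trial cannot be stated, because the mix of tumour sites is unknown. The absence of a one-year post-surgery score is independent of these assumptions. Primary conclusions on toxicity and on 6-month non-progression are unaffected.

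**What to change.** 1. Confirm that an upper-limb page of Appendix 7 exists. If it does not, add the section 9.1 upper-limb items to the form and the eCRF. Score each patient on the form for the affected limb.
2. For trunk-wall patients, report the applicable common items only, with no total.
3. Do not count the surgery-acceptance item in scores taken without surgery. Report the total as a percentage of the applicable maximum (30 points, or 25 without that item), and base any change on the same items at both times.
4. State whether the 10 points are raw or percentage points. On a six-item score, 10 raw points are 33% and 10 percentage points are 3 raw points, so the choice changes the result and should be made before the data are examined.
5. Describe results by tumour site. Anatomic location is already tabulated at baseline (SAP Table 3.3).
6. Reconcile the comparison of before surgery with one year after surgery with the schedule: either plan an MSTS at one year or remove the comparison from both documents.

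The cost is one form page, a few eCRF items and some SAP wording, plus one further assessment if the one-year comparison is kept. The downside is small groups: at most 41 patients divided by site allow description only. Dropping an item and rescaling also modifies the instrument, which the report should say.

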^b NFS, MCV, MCHC, MCH, Albumin, alkaline phosphatase, total bilirubin, urea, calcium, creatinine, fasting glucose, LDH, potassium, magnesium, total protein, SGOT [AST], SGPT [ALT], GGT, sodium, TP, INR, CPK

^c repeated within 24 hours if > 470msec

^d Every 3 months until death or study termination.

^e: to be done on Day 28

^f could be continued until progression at the investigator's discretion and sponsor authorization

^g at baseline, at D8 before radiotherapy initiation and week 12

^h within 28 days prior to the start of study treatment

ⁱ If Olaparib is continued, visit each month: Week 16 and 20, etc

^j Completed by the radiotherapist at baseline and at the end of radiotherapy treatment

^k: Every 8 weeks

^l: if applicable

LIST OF ABBREVIATIONS AND DEFINITION OF TERMS

ADP	Adenosine Diphosphate
AE (s)	Adverse Event (s)
ALT	Alanine Aminotransferase
ANC	Absolute Neutrophil Count
ANSM	Agence Nationale de sécurité du Médicament
AP	Alkaline Phosphatase
aPTT	Activate Partial Prothrombin Time
AST	Aspartate Aminotransferase
CI	Confidence Interval
CPP	Ethic Committee
CR	Complete Response
CRA	Clinical Research Assistant
CrCL	Creatinine Clearance
CRF	Case Report Form
CT	Computerized Tomography
DLT	Dose Limiting Toxicity
DNA	Deoxyribonucleic Acid
DQF	Data Query Form
DSB	Double-Stranded Binding
ECG	Electrocardiogram
ECOG	Eastern Cooperative Oncology Group
EMA	European Medicines Agency
EMEA	European Medicines Evaluation Agency
FFPE	Formalin-Fixed Paraffin-Embedded
FUP	Follow-Up
GCP	Good Clinical Practice
GGT	Gamma Glutyl-transferase
HCG	Human Chorionic Gonadotropin
HIV	Human Immunodeficiency Virus
HNSCC	Head and Neck Squamous Cell Carcinoma
HR	Homologous Recombinaison repair
IB	Investigator Brochure
ICF	Informed Consent Form
ICH	International Conference on Harmonization
IDMC	Independent Data Monitoring Committee
IEC	Institutional Ethics Committee
IHC	Immunohistochemistry
IMP	Investigational Medical Product
INR	International Normalized Ratio
IRB	Institutional Review Board
IrEICS	Events of Clinical Interest Immune-related
IUD	IntraUterine Device
LDH	Lactate Dehydrogenase
MAD	Maximum Administered Dose
MedDRA	Medical Dictionary for Regulatory Activities
MRI	Magnetic Resonance Imaging
MTD	Maximum Tolerated Dose
NCI-CTCAE	National Cancer Institute Common Terminology Criteria for Adverse Events
NHEJ	Non-Homologous End Joining
NPR	Non Progression Rate
NSCLC	Non-Small Cell Lung Cancer
OS	Overall Survival
PD	Progressive Disease
PFS	Progression Free Survival

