3.4.1. Treatment scheme and DLT observation period

- Olaparib will be given orally, continuously, twice a day, as appropriate for assigned dose level, from D1 to the end of radiotherapy. Olaparib will be started one week before the start of radiotherapy and will be continued until the last day of radiotherapy. Beyond this period, Olaparib could be continued until progression, at the investigator's discretion and sponsor approval.
- Radiotherapy consists of fractionated focal irradiation at a dose of 1.8 Grays (Gy) per fraction given once daily five days per week (Monday through Friday), for a total dose of 59.4 Gy (i.e 33 fractions). Radiotherapy starts at D8.
- The DLT observation period is defined as the first day of Olaparib intake and up to 6 weeks after the end of radiotherapy (13.5 weeks).

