In case of surgery, post surgery complications must be reported during 12 months after the surgery unless start of a new anti-tumor therapy.

5.7.FOLLOW-UP AFTER END-OF-TREATMENT VISIT

- Each patient will be followed-up for 12 months after inclusion.
- The date and reason of the study discontinuation will be recorded on the patient's CRF (see Section 5.2).
- After treatment discontinuation, patients will be followed every 3 months until death or until the end of the follow-up period, whichever occurs first.
- Patients who withdraw consent will not be followed with any study procedures.

All AEs (including SAEs) suspected to be treatment-related (Olaparib and/or radiotherapy) or research-related will be followed-up until the events or their sequelae resolve or stabilize at a level acceptable to the Investigator and the Sponsor.

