7.2.5. Adverse effects management

Acute toxicities of radiotherapy of STS are essentially musculoskeletal or cutaneous toxicities. They will be evaluated through a clinical examination performed each week during radiotherapy and one month after the end of radiotherapy (D8, D15, D22, D29, D36, D43, D50, D64, D78, D92) or until regression of a grade 3. Grading of adverse events will be done according to the CTCAE v.4.

- If a grade ≥ 3 musculoskeletal or cutaneous toxicity is observed before a radiotherapy dose of 30Gy, Olaparib and radiotherapy were stopped (DLT) but radiotherapy could be continued when regression to a grade ≤ 2 will be achieved.
- If a grade ≥ 3 musculoskeletal or cutaneous toxicity is observed after a radiotherapy dose of 30Gy, radiotherapy will be stopped until regression to a grade ≤ 2 and then will be continued. Olaparib will be continued during radiotherapy interruption. If grade ≥ 3 persits more than 4 weeks, Olaparib will be stopped (DLT).

The irradiated skin area that will be included in the operative volume must be identified during contouring and protected during planification (ALARA) in order to limit the occurrence of post-operative acute cutaneous and mucous complications [30 - 31].

7.3.ASSOCIATED TREATMENT: SURGERY FOR RESECTABLE DISEASE

Surgery will be performed by expert surgeon within 12 weeks of radiotherapy completion in reference centers labelled by the French NCI and NETSARC network.

Post-operative complications will be recorded up to 12 months after surgical complication.

Surgical sample will be analyzed to determine histological response and data will be collected in case report form.

The decision of surgery has to be taken by the investigational site during Multidisciplinary Tumor Board (RCP),

The decision of surgery has to be notified to the sponsor as soon as possible (i.e. before surgery).

Post-surgery clinical exam: addition of 3 visits after surgery (D30, D60 and D90). The next visits remain unchanged (follow-up every 3 months).

Post-surgery complications grade 3 should be reported immediately as serious adverse event to the Vigilance Unit of the Sponsor.

CONFIDENTIAL

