Overall Survival (OS)	END OF TREATMENT DT_STA (Date of start of Olaparib) EOT_STA (Status) EOT_REA (Reason end) FOLLOW UP FORM DT_LNEW / DT_DEAT STA_FUP (Vital status) END OF STUDY (END_STU) DT_EOS (date of end of study) EOS_REA (reason) DT_DEATH (date of death)	If (STA_FUP NE 'dead') then do; if (EOS_REA='death') then { OS= DT_DEATH-DT_STA; IND_OS=1; } Else {OS= DT_EOS-DT_STA; IND_OS=0; } end; Else { OS= DT_DEAT-DT_STA; IND_OS=1; }
Functional assessment	EXA_RAD MSTS_RA (msts score)	Check if MSTS_RA is completed by the radiotherapist at baseline and at the end of radiotherapy treatment.

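### The MSTS comparison of before surgery with 1 year after surgery has no scheduled post-surgery score, and the plan does not say which score is the pre-surgery one

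*Protocol*

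**What the plan says.** Protocol 9.1 sets out the MSTS analysis in two parts. The total score is described at each measurement time, and "A difference of 10 points or more will be used to define a clinically significant difference". It then adds: "There is particular focus on the difference between the observed scores before surgery and 1 year post surgery". SAP 3.2.2.1 repeats this text.

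On collection, protocol 9.1 says: "MSTS will be completed by the radiotherapist at baseline and at the end of radiotherapy treatment". Footnote j of the assessment schedule and the table in protocol 5.5 give the same two times, as does the data check in the SAP.

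On surgery, protocol 7.3 says: "Surgery will be performed by expert surgeon within 12 weeks of radiotherapy completion". It adds clinical visits 30, 60 and 90 days after the operation, followed by the usual three-monthly visits. MSTS is not mentioned at any of them.

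On follow-up, protocol 5.7 says: "Each patient will be followed-up for 12 months after inclusion". Footnote d of the schedule instead has three-monthly visits that end only at death or the close of the study.

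Protocol 2.2.2 makes functional assessment a secondary objective of the expansion cohort. The expansion endpoints in protocol 9.2 and SAP 3.2.2.2 leave it out.

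**The concern.** Both documents single out one functional comparison, and its second value has no place in the schedule. If nothing changes, that comparison returns no result. Operated patients would then have no functional outcome after their operation. An assessment not made at the time cannot be recovered at analysis.

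The first value is also loose. Two scores precede surgery, one before any treatment and one after radiotherapy with olaparib. They answer different questions: change from the untreated state, or change attributable to the period from surgery onward. Leaving the choice open until the data are seen is avoidable.

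The gap is most relevant in the expansion cohort, which has a defined resectable group (protocol 3.5 and 7.2.4) and whose endpoint list omits function.

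**Working it through.** **1. When MSTS is collected**

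| Source | Times | After surgery |
|---|---|---|
| Protocol 9.1 | baseline, end of radiotherapy | none |
| Schedule footnote j and protocol 5.5: "Completed by the radiotherapist at baseline and at the end of radiotherapy treatment" | same | none |
| SAP 3.2.2.1, endpoint text | same | none |
| SAP 3.2.2.1, data check: "Check if MSTS_RA is completed by the radiotherapist at baseline and at the end of radiotherapy treatment" | same | none |

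Surgery follows radiotherapy, so by the text both scores come before it. There is one caveat. In the extracted schedule the second MSTS mark seems to stand at week 10 (D64), which could fall after an early operation. That table may be broken in extraction, so I rely on the text.

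**2. When 1 year after surgery falls**

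The plan's own figures reproduce. From protocol 3.4.1, "Radiotherapy starts at D8". With D8 a Monday and five fractions a week, fraction 33 falls on 8 + 7×6 + 2 = D52, as the synopsis states. Enrolment plus last follow-up is 56 + 12 = 68 months, as protocol 5.1 states.

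Other inputs:
- The resectable schedule has 25 fractions (protocol 7.2.4), so the last falls on 8 + 7×4 + 4 = D40.
- Surgery comes 0 to 84 days after the last fraction: D40–D124 (25 fractions) or D52–D136 (33 fractions).
- Treatment starts 0 to 7 days after registration (protocol 6.2).

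Months from inclusion to 1 year after surgery = (surgery day − 1 + 365.25 + lag) / 30.4375.

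| Schedule | Earliest | Latest |
|---|---|---|
| 25 fractions | (39 + 365.25 + 0)/30.4375 = 13.3 | (123 + 365.25 + 7)/30.4375 = 16.3 |
| 33 fractions | (51 + 365.25 + 0)/30.4375 = 13.7 | (135 + 365.25 + 7)/30.4375 = 16.7 |

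**3. Whether patients are seen then**

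- *Follow-up stops 12 months after inclusion (protocol 5.7).* The time point is missed by 13.3 − 12 = 1.3 to 16.7 − 12 = 4.7 months. At month 12 an operated patient is between (365.25 − 39)/30.4375 = 10.7 and (365.25 − 7 − 135)/30.4375 = 7.3 months past surgery. No operated patient reaches 1 year.
- *Follow-up runs to the close of the study (footnote d).* With closure at month 68, a patient included by month 68 − 16.7 = 51.3 (latest case) to 68 − 13.3 = 54.7 (earliest case) reaches it. Assuming uniform accrual over 56 months, that is 51.3/56 = 92% to 54.7/56 = 98% of all patients. For the last 15 of 41, who would enter from month 56×26/41 = 35.5, it is (51.3 − 35.5)/20.5 = 77% to (54.7 − 35.5)/20.5 = 94%.

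Under either rule the number of planned post-surgery MSTS scores is zero.

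**The case against.** The best defence is that the stated objective is functional assessment before and after treatment. The two scheduled scores serve that, and the first analysis item, describing the total at each measurement time, can be carried out as written. Only one sentence is unsupported. This stands, and it limits the point: a reader might infer that the whole functional analysis would return nothing, and that is not so.

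Three other stronger readings are tempting.

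- *Neither score is scheduled.* This is not supported. Both scheduled scores normally precede surgery, so a pre-surgery value exists. What is missing is a statement of which one it is.
- *Follow-up ends too early for every operated patient.* This is true only if protocol 5.7 is read as a cap. Footnote d has no such cap, protocol 5.6 and 11.5 require complications to be reported for 12 months after surgery, and the SAP synopsis gives 1 year as a minimum. The SAP synopsis is the weakest of these, since its enrolment period (24 months) is not the protocol's (56). The documents conflict, and the contrast fails because no form is scheduled, whichever rule applies.
- *The 10-point threshold is on an unstated scale.* Six items scored 0 to 5 give a total of 0 to 30, and neither document mentions any other scale. I raise nothing there.

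**Conclusion.** The comparison that both documents emphasise cannot be computed in any operated patient from the planned data, because no MSTS score is scheduled after surgery. This rests on the text alone and needs no assumption about dates. In addition, the pre-surgery score is not identified, the follow-up passages disagree on whether a visit at 1 year after surgery exists, and the expansion endpoint lists omit an objective set for that cohort.

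The figures of 13.3 to 16.7 months assume a Monday start of radiotherapy, no interruption, and surgery within the 12-week window. The 77% to 98% range also assumes uniform accrual and closure at month 68. It describes who could be seen, not who would be operated on or scored.

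The endpoint is secondary and descriptive. Sample size, dose decisions and the primary analyses are untouched. It should be corrected, but it does not threaten the trial's main conclusions.

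**What to change.** 1. In protocol 9.1 and SAP 3.2.2.1, name the pre-surgery value: the end-of-radiotherapy score, or the last score before surgery.
2. Then choose one of two routes.
   - *Keep a surgical contrast.* Add the MSTS form for operated patients at day 90 after surgery and at the three-monthly visit nearest 12 months after surgery, and define the contrast on those visits. Day 90 is reachable under either follow-up rule: at the latest it falls (135 + 90 + 7)/30.4375 = 7.6 months after inclusion. The 12-month visit first needs protocol 5.6, 5.7 and 11.5, footnote d and the SAP synopsis to be reconciled. With three-monthly visits the nearest one lies within about 3/2 = 1.5 months of the target, so a window should be stated.
   - *Drop it.* Replace the sentence in both documents with within-patient change from baseline to end of radiotherapy.
3. Add functional assessment to protocol 9.2 and SAP 3.2.2.2. The list of tables in SAP 4.2 has no MSTS table and needs one.

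The cost is wording in both documents and, on the first route, one short form at visits that already take place. The second route costs no data collection but leaves operated patients without a post-surgical functional outcome.
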